- Currently prescribed one of the following adjuvant chemotherapy regimens: (IV 5-fluorouracil [5-FU] / leucovorin [LV], capecitabine, FOLFOX [5-FU, LV, oxaliplatin], CAPOX [capecitabine and oxaliplatin]
 - Patients must have started chemotherapy or plan to start, with planned receipt of the first exercise visit **by the third infusion visit**.
 - Patients receiving FOLFOX chemotherapy are eligible to enroll in the pharmacokinetics sub-study (see section 3.10).
- No planned major surgery anticipated in the intervention period
- Sufficient time to heal from any major surgery to start of intervention, including colostomy reversal (port-a-cath removal excluded)
- Creatinine value < 2 mg/dL
- Approval by either oncologist or surgeon to participate in trial
- Readiness (as determined by the Physical Activity Readiness Questionnaire (PAR-Q) – see Appendix 13.2.2)
 - If there are any indications that home based exercise would be unsafe based on PAR-Q the patient will not be enrolled until confirmation from the patient's treating provider is received via email and/or phone that they are safe to exercise. Provider does not need to be contacted if patient answers 'yes' to 'Is your doctor currently prescribing any medication for your blood pressure or for a heart condition?'
- Ability to understand and the willingness to sign a written informed consent document in English
- Willingness to be randomized

3.4 Exclusion criteria:

- Concurrent actively treated other cancer (except non-melanoma skin cancer, in situ cervical cancer or localized prostate cancer treated with surveillance only)
- Patients with untreated hypertension (> 180 mm Hg systolic or > 100 mm Hg diastolic) appearing in the patient's medical record in the two weeks prior to screening will not be enrolled until confirmation from the patient's treating provider is received via email and/or phone that they are safe to exercise.
- Presence of metastatic disease
- Current strength training ≥ 2 x week for the past 3 or more months
- Patients enrolled in other clinical trials of weight loss, physical activity or dietary interventions are ineligible.

3.5 Inclusion of women and minorities:

We seek to recruit 180 participants with a diagnosis of colon cancer. We will not exclude any participants due to their race and ethnicity. All races are accepted. The distribution of

participants by race and ethnicity is expected to mirror that of the institution's colon cancer patient population.

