			Day 1																												28 Weeks															
sLV5FU2 Leucovorin, followed by 2 day continuous infusion 5FU, repeated every 2 weeks	2 days	12 cycles	IV		IV		IV		IV		IV		IV		IV		IV		IV		IV		IV		IV		IV																			
			Day 1																				20 Weeks																							

INTERVENTION
DRUG
VISIT

A research assistant will either conduct eConsent over the phone or by video conference or meet the participant in person to complete the consent forms. The baseline visit will most likely occur as an add-on to the first or second chemotherapy infusion session or another clinical appointment, so as to avoid the need for additional visits to the clinic or cancer center for the study. If scheduling of the baseline or follow-up visits at the clinic is not convenient for the participant, the research assistant will also be available to conduct these study visits at the participant's home.

After the participant consents to be in the study (see Appendix 13.3), we will complete questionnaires with the participant as part of the baseline visit (e.g. physical activity assessment and physical function testing, see Appendix 13.5, FFQ, see Appendix 13.6.1, SF-36, and demographics, see Appendix 13.4), as well as a patient-completed side effects questionnaire

(see Appendix 13.7.3). In addition, body composition will be assessed using anthropometrics collected at the baseline visit, a DXA (see Appendix 13.8) to be scheduled as soon as possible, prior to initial intervention, and creatine dilution (see Appendix 13.8.3). Also, at the baseline visit, we will arrange for research blood draw, when possible to be coordinated with clinical blood draw that the patient receives as part of clinical care (either that visit or next chemotherapy visit but prior to starting intervention).

3.8 Interventions for experimental group:

Table 4. Intervention Terminology

Chemotherapy Cycle	A cycle of chemotherapy from infusion visit to the next infusion visit, usually this will be 2-3 weeks
Chemotherapy Infusion Visit	Date on which the participant receives chemotherapy infusion at the cancer/medical center.

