9. STATISTICAL CONSIDERATIONS

9.1 Study design:

This randomized controlled trial of resistance training intervention in colon cancer patients receiving chemotherapy consists of two arms: an in-person and telephone-based intervention to promote home-based resistance training, and a wait-list, control group. After consent and baseline visit measurements, randomization assignment will utilize a covariate adaptive randomization procedure which ensures that equal numbers of patients are assigned to each study arm and that the two arms remain balanced on five key characteristics: site of participation [Kaiser Permanente vs Penn State vs Dana-Farber]; gender [male vs female]; cancer stage [stage II vs stage III], and duration of chemotherapy [3 months vs 6 months]; planned chemotherapy regimen [FOLFOX vs CAPOX vs capecitabine vs 5-FU/LV]. This randomization method (also known as the minimization method) has been demonstrated to outperform simple randomization or stratified randomization in terms of achieving balanced groups, particularly in smaller trials with multiple important prognostic factors.

The primary objective of this trial is to compare the effect of a RT intervention versus a wait-list control on chemotherapy dose reductions, dose delays, early discontinuation of chemotherapy and treatment-related toxicity. The secondary objective is to compare the effect of the intervention versus wait-list control on changes in inflammatory biomarkers, and the tertiary objective is to compare pre and post intervention pharmacokinetics of 5-FU and oxaliplatin. The d3 Creatine objective is to compare the effect of a RT intervention versus a wait-list control on d3 creatine muscle mass at 6 months.

9.2 Sample size, accrual time and study duration:

One hundred and eighty (180) participants will be recruited and randomized over a total of 3.5 years. Patient involvement and data collection will last approximately 6 months.

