### **2.2 Analysis of primary endpoints**

## Statistical Analysis Plan

FORCE: Focus on Reducing Dose-Limiting Toxicities in Colon Cancer with Resistance Exercise

All data analyses will be by intent-to-treat. Multiple linear regression will be used to assess the difference between the RT and UC groups in RDI. We will analyze RDI individually for each drug and then across all chemotherapy regimens combined. We will use logistic regression to examine the commonly used cut points < 85% and <70% RDI as outcomes.

We will assess the difference between RT and UC groups in self-reported treatment toxicities in three ways:

- A. as a binary variable with yes as the occurrence of any of one of 8 symptoms that are reported as moderate or severe over the course of chemotherapy in RT vs. UC. We will exclude the PRO-CTCAE muscle ache item from the composite score (will be reported separately), since that is believed to be related to the performance of the resistance training intervention. We'll utilize logistic regression for point and interval estimation of odds ratios, RT vs. UC, for any (i.e., one or more) of 8 symptoms reported as moderate severe, for each symptom individually, and finally in groups of similar symptoms, such as gastrointestinal issues;
- B. as the number of the 8 symptoms reported as moderate or severe at least once over the course of chemotherapy in RT v. UC (a count ranging from 0-8). We will use Poisson regression with allowance for overdispersion for point and interval estimation of relative differences (rate ratio) in the mean total number of moderate or severe toxicities reported at least once over the course of chemotherapy; and
- C. as longitudinal analyses of number of moderate or severe toxicities reported per cycle in relation to randomization arm (RT vs. UC) and time since randomization using Poisson regression with allowance for overdispersion. Generalized estimation equations (GEE) will be used for model parameter estimation to account for within person correlation in repeated measures. The main effect for randomization arm is interpreted as the average treatment effect over the time. Heterogeneity in effect over time will be assessed by inclusion of randomization arm by time-interaction terms.

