In addition to treatment arm, each model will include covariates used in the randomization procedure (study site, treatment duration, treatment regimen, gender, stage). Exploratory analyses will examine the impact of including additional (not pre-specified) covariates in estimation of treatment effect, with a focus on variables with chance imbalance in distributions by treatment group. Analyses resulting in an appreciable change in the estimate of between-group differences or increase in precision of the treatment effect will be noted.

We will also conduct analyses stratified by sex, frailty status and duration of the intervention, excluding the strata-variable from the covariate list (i.e., exclude gender in analysis by men and women) by inclusion of appropriate cross product terms in regression models. Exploratory analyses will additionally assess heterogeneity in treatment effect on study outcomes by exercise adherence.

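### Toxicity analyses A–C prespecify no baseline symptom or prior-chemotherapy covariate, although both are recorded before randomization; the cost is precision and dilution, not bias

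*SAP*

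**What the plan says.** **Outcomes (SAP 2.2).** Analysis A is binary: any of eight symptoms moderate or severe. Analysis B is the "number of the 8 symptoms reported as moderate or severe at least once over the course of chemotherapy". Analysis C is described as "longitudinal analyses of number of moderate or severe toxicities reported per cycle in relation to randomization arm (RT vs. UC) and time since randomization", fitted by GEE Poisson regression. None of the three subtracts, excludes or conditions on symptoms present at baseline.

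**Covariates (SAP 2.2).** The plan states that "each model will include covariates used in the randomization procedure (study site, treatment duration, treatment regimen, gender, stage" are used. It then adds that "Exploratory analyses will examine the impact of including additional (not pre-specified) covariates in estimation of treatment effect", focusing on variables that happen to be imbalanced, and that a material change in the estimate or a gain in precision will be noted.

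**Timing (Protocol 3.3, 3.7).** The inclusion criterion reads "Patients must have started chemotherapy or plan to start, with planned receipt of the first exercise visit" by the third infusion visit, so zero, one or two infusions may come first. Section 3.7 adds: "The baseline visit will most likely occur as an add-on to the first or second chemotherapy infusion session".

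**Baseline data (Protocol 3.7, Table 7, 4.11, 9.1).** The baseline visit includes questionnaires "as well as a patient-completed side effects questionnaire". Section 9.1 fixes the order: "After consent and baseline visit measurements, randomization assignment will utilize a covariate adaptive randomization procedure". Section 4.11 records the start date of each cycle, so prior infusions can be counted. Table 7 schedules no PRO-CTCAE at baseline.

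**Contrast with the dose endpoint.** SAP 1.1 starts the RDI calculation at the first cycle after randomization, and Protocol 4.11 counts only dose reductions after the intervention starts. Analyses A and B state no such start.

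**The concern.** Participants have had a curative-intent resection, and some will already have had chemotherapy. Pain, fatigue, diarrhea and numbness are all scored, and Protocol 1.3 describes oxaliplatin neuropathy as partly cumulative. Symptom burden at entry and infusions already received are therefore plausible predictors of later reports. Three things follow if the models ignore them.

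- Variation between patients that existed before randomization stays in the error term.
- A chance difference between arms in baseline symptoms passes into the odds and rate ratios.
- A symptom that was already moderate or severe and is reported again counts as an event that the intervention had no chance to prevent. This pulls the effect towards no difference.

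Toxicity is a primary endpoint and the sample is fixed at 183 (SAP 2.1), so covariates are one of the few remaining sources of precision.

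**Working it through.** **1. Reproduce the plan's figure.** Inputs from Protocol 9.3.4 and SAP 2.1: 90 per arm, two-sided alpha .05, power .80, .42 SD.
- Normal approximation: (1.960 + 0.842) × √(2/90) = 0.418 SD.
- t-test: 0.420 SD, with power .800 at .42 SD.
- On the RDI scale: .42 × 17.3 = 7.27, against the stated 7.3.

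The protocol's figure is thus an unadjusted comparison of means on the full sample.

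**2. Linear illustration of a baseline covariate.** With baseline–outcome correlation r, the residual SD is multiplied by √(1 − r²). The equivalent gain in patients is 1/(1 − r²). The documents give no r, so a range is shown.

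| r (assumed) | 1/(1 − r²) | Power at .42 SD | Detectable difference, 0.418 × √(1 − r²) |
|---|---|---|---|
| none | 1.00 | .80 | 0.42 |
| .2 | 1.04 | .82 | 0.41 |
| .3 | 1.10 | .84 | 0.40 |
| .5 | 1.33 | .90 | 0.36 |
| .6 | 1.56 | .94 | 0.33 |

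**3. Simulation of analysis B.** Overdispersed Poisson regression, 92 v 91 patients, 600 runs per setting. Assumptions, none from the documents: eight symptoms; a normal person effect; 40% control incidence for the average patient; log-odds effect −0.5; baseline moderate or severe symptoms always counted in the outcome; baseline items that match the outcome exactly. The minimization factors were in neither model.

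| Baseline prevalence per symptom | Person SD 0.7: power without → with term | Person SD 1.2: without → with |
|---|---|---|
| 5% | .84 → .89 | .51 → .62 |
| 10% | .75 → .87 | .43 → .64 |
| 20% | .57 → .81 | .33 → .56 |

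With no treatment effect, rejection was .03–.06 with and without the term. The gain is therefore in precision and does not correct a bias. Full carry-over and exact matching favor the covariate, so these gains are at the generous end.

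**4. Dilution.** Let q be the share of symptoms already present and counted, p = .30 the control incidence of new symptoms, and 0.75 the risk ratio for new symptoms. The observed ratio is [q + (1 − q) × p × 0.75] / [q + (1 − q) × p].
- q = .10: .3025/.37 = 0.82.
- q = .20: .38/.44 = 0.86.

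The covariate does not undo this. In the simulation with person SD 0.7, the rate ratio was .776, .805 and .852 without the term, and .776, .805 and .851 with it.

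**5. Analysis A behaves differently.** Take the same inputs and treat the eight symptoms as independent. The proportion with any symptom is 1 − (1 − c)⁸, where c is the per-symptom risk.
- q = 0: .942 v .870, power about .38 with 90 per arm.
- q = .10: .975 v .944, power about .18.
- q = .20: .990 v .978, power about .10.

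The outcome is near its ceiling, so the .80 starting point in step 2 does not describe A. If baseline symptoms also count as events, every patient with a nonzero matched baseline score is an event. Ordinary logistic regression then quasi-separates on that term.

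**The case against.** **There is no validity error.** Correct. Allocation is randomized, the minimization factors are a defensible primary covariate set, and the null rejection rates confirm it. A reader might infer that omitting a baseline term biases the comparison. The documents do not support that.

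**The SAP already deals with it.** In part. The exploratory clause could admit a baseline score and says that gains in precision will be noted. But it covers only covariates that are not prespecified, and it looks to observed imbalance and the effect on the estimate. A strongly prognostic baseline measure should be named in advance whether or not it is imbalanced.

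**There is no baseline value of the outcome.** This stands. Table 7 has no baseline PRO-CTCAE, and the items of the side-effects questionnaire are in an appendix that was not available. Apart from PRO-CTCAE, the only instrument that Protocol 4.12 describes concerns neurotoxicity. If the questionnaire is mostly that, its total may correlate only weakly with an eight-symptom count.

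**The baseline questionnaire may be late or missing.** This stands. Table 7 footnote 4 allows web, telephone or paper forms posted back within three days, so some may be absent or completed after randomization.

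**The size is assumed.** This stands. At r = .2 the gain is about 2 points of power. The linear formula does not transfer directly to overdispersed Poisson models, and it does not transfer to A. The SAP models already include regimen and duration, so the partial correlation after those terms is what matters.

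**Pre-existing symptoms count only if reported again.** Largely fair. Protocol 4.12 places PRO-CTCAE collection during the intervention, and eligibility requires time to heal from major surgery. The SAP still gives A and B no start date.

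**Conclusion.** The point holds as a matter of efficiency and outcome definition. A–C omit a baseline symptom score and the number of prior infusions, both scheduled or recorded before randomization. The consequences are lost precision, exposure to chance baseline imbalance, and dilution where existing symptoms are reported again.

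The size cannot be fixed from the documents. For a linear comparison at .42 SD with 90 per arm, the gain runs from about 2 points of power (r = .2) to about 14 (r = .6). The simulation of B agrees in direction under favorable assumptions. C was not simulated.

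Two stronger readings should be resisted. One is that adding a covariate stops pre-existing symptoms from counting as outcome: it leaves the outcome unchanged, and the simulated rate ratio did not move. The other is that a rise from .80 to as much as .94 can be expected for all three analyses: r is unreported, A is near its ceiling, and the existing covariates may already capture part of the gain.

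**What to change.** 1. **B and C.** Prespecify two covariates: the baseline side-effects score (matching items where they exist, otherwise the total) and the number of infusions before randomization (0, 1, 2; cycles started for oral capecitabine). Give a simple rule, such as a missing indicator, for questionnaires that are absent or completed after randomization.
2. **Outcome window.** State that A and B count only reports made after randomization, in line with the RDI definition in SAP 1.1.
3. **Dilution.** Where items match, add a sensitivity analysis that counts only symptoms new or worse than baseline.
4. **A.** Use the same covariates with a penalized or standardized estimator and report a marginal risk difference beside the odds ratio. Ordinary logistic regression may quasi-separate, and covariate adjustment changes the meaning of the odds ratio.
5. **Check first** which of the eight symptoms the baseline questionnaire covers.

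The cost is SAP wording, two model terms, a missing-data rule and one sensitivity analysis. No new data collection is needed, but completeness and timing of the baseline questionnaires must be checked. The change should be dated before toxicity is compared by arm; if that comparison has been made, the adjusted results should be labeled post hoc.

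### Toxicity analysis C does not say that its arm-by-time test allows for an effect that differs by planned chemotherapy duration, so such a difference could be read as change over time

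*SAP*

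**What the plan says.** Analysis C in SAP 2.2 covers "longitudinal analyses of number of moderate or severe toxicities reported per cycle in relation to randomization arm (RT vs. UC) and time since randomization". The model is Poisson with allowance for overdispersion, and "Generalized estimation equations (GEE) will be used for model parameter estimation to account for within person correlation in repeated measures". The working correlation is not named. Two sentences govern interpretation: "The main effect for randomization arm is interpreted as the average treatment effect over the time", and then "Heterogeneity in effect over time will be assessed by inclusion of randomization arm by time-interaction terms".

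Duration appears twice more in SAP 2.2. As a covariate: "each model will include covariates used in the randomization procedure (study site, treatment duration, treatment regimen, gender, stage". As a possible effect modifier: "We will also conduct analyses stratified by sex, frailty status and duration of the intervention", carried out "by inclusion of appropriate cross product terms in regression models". The second statement is not attached to analysis A, B or C, and it does not mention the arm-by-time test.

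Protocol 9.1 lists "duration of chemotherapy [3 months vs 6 months" among the minimization factors. SAP 1.2 ties each PRO-CTCAE report to a chemotherapy cycle, so a patient stops contributing when chemotherapy stops.

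**The concern.** The set of patients who report changes with time since randomization. Early reports come from everyone; late reports come from patients on longer regimens. A main effect for duration moves the toxicity level of both arms together. It does not let the arm effect differ by duration. If that effect does differ, the pooled arm effect shifts as the 3-month patients leave, and the arm-by-time term is the only one in the model that can absorb the shift.

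What is at stake is the interpretation of the time course. A report that the benefit builds up or fades during chemotherapy could arise from who is left in the data, with no change in any patient. The test stands under the analysis of primary endpoints and the SAP does not label it exploratory, so it is likely to be reported.

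**Working it through.** **1. The plan's own figures.** None is given for analysis C. Protocol 9.3.4 covers two-arm comparisons of means, and its figures reproduce: 0.42 × 17.3 = 7.27 (stated as 7.3%); power at 90 per arm for 0.42 SD is 0.804; the minimum detectable difference at 81 per arm is 0.443 SD (stated as 0.44). They do not bear on this test.

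**2. Who reports when.** From Protocol Table 3:
- 3-month FOLFOX: 6 × 14 = 84 days; 3-month CAPEOX: 4 × 21 = 84 days. Both are 12 weeks.
- 6-month FOLFOX: 12 × 14 = 168 days; 6-month CAPEOX: 8 × 21 = 168 days. Both are 24 weeks.
- The table marks 8-week windows for the 3-month regimens and 18 to 28 weeks for the others.

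So from about 8–12 weeks after randomization, delayed cycles apart, only patients on longer regimens report.

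**3. Mechanism.** Let w(t) be the share of expected control-arm toxicities at time t that comes from 3-month patients, and let RR3 and RR6 be rate ratios that are constant over time. The pooled ratio is

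RR(t) = w(t) × RR3 + (1 − w(t)) × RR6.

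Take half the patients in each group and equal control means, so that w = 0.5 early and 0 late:
- RR3 = 1.0, RR6 = 0.75: early 0.5 × 1.0 + 0.5 × 0.75 = 0.875; late 0.75.
- RR3 = 1.0, RR6 = 0.60: early 0.80; late 0.60.
- RR3 = RR6: RR(t) is constant whatever w(t) is.

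**4. Simulated size.** From the documents: 183 patients (92 and 91), one report per cycle, two-sided 5% level. Assumed: control mean 1.5 toxicities per report, gamma between-patient variance 0.4–0.5, 3-month share 30–70%, the rate ratios, and the working correlation. The true effect is constant over time within each duration group, and the fitted model has duration as a main effect. Arm-by-time rejection:

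| RR, 3-month / 6-month | 3-month share | Runs | Independence | Exchangeable |
|---|---|---|---|---|
| 1.0 / 1.0 | 50% | 1000 | 6.1% | 5.2% |
| 0.8 / 0.8 | 50% | 1000 | 5.4% | 5.3% |
| 0.75 / 0.85 | 50% | 200 | 11% | 6.5% |
| 1.0 / 0.75 | 50% | 300 | 17.0% | 9.0% |
| 1.0 / 0.70 | 30, 50, 70% | 1000 each | 18.7, 24.9, 25.7% | 7.5, 8.0, 6.7% |
| 0.70 / 1.0 | 50% | 1000 | 22.6% | 8.5% |
| 1.0 / 0.60 | 50% | 300 | 42.7% | 13.7% |
| 1.0 / 0.50 | 30, 50, 70% | 1000 each | 49.8, 67.2, 67.0% | 13.3, 14.0, 13.7% |

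A further 250-run set, also with 183 patients and assumed inputs, gave 19% and 9% for 1.0 / 0.75, and 45% and 7% for 1.0 / 0.60. The sets differ in inputs and in simulation error: at 250 runs, the standard error of a 10% rate is √(0.10 × 0.90 / 250) = 1.9 percentage points.

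**5. Apparent drift, weeks 0 to 20.**
- Independence: 0.89 to 0.71 for 1.0 / 0.75; 0.83 to 0.54 for 1.0 / 0.60.
- Exchangeable: 0.90 to 0.85 and 0.83 to 0.74. For 0.75 / 0.85 it is 0.79 to 0.82.

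Exchangeable weighting relies more on change within patients, and here there is none.

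**6. With the extra terms.** Adding arm by duration alone gave rejection of 5.7–7.3% (300-run set) and 3–7% (250-run set), with a mean slope of about 0. Adding arm by duration and time by duration gave 5.0–6.8% (1000-run set), with an estimated change in rate ratio of 0.998–1.002 per month, under both working correlations.

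**The case against.** The strongest reply is that the SAP already holds the remedy. The duration-stratified analyses with cross-product terms sit in the same section as A to C and are not limited to A or B; applied to analysis C, they supply the missing term. That largely stands. A reader might infer that duration is nowhere more than a main effect, and the SAP does not support that. What remains is the missing link: the stratified analyses are introduced as additional work, and nothing says the arm-by-time test is read from a model that contains their terms.

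The second reply is that no effect difference by duration is documented. This is correct. Planning a subgroup analysis does not predict a difference, and with a common effect the test behaves properly. The first two rows of the table show this.

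Third, GEE was chosen to handle within-person correlation, so independence may not be what the statistician intends. That is fair, and under exchangeable the distortion is modest. But GEE with an independence structure and robust standard errors is also a valid way to account for correlation, and the SAP names neither.

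Fourth, a GEE effect is population-averaged: among patients still on chemotherapy late on, the average rate ratio would truly differ from the early one. This also stands. The error lies in reading that as change within patients, which the SAP neither states nor rules out.

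**Conclusion.** The point holds as a gap in specification. Run as written, the arm-by-time test in analysis C can present an effect that differs by planned duration as one that changes over time. The direction follows from the reporting schedule. The size rests on assumed rates, between-patient variance, duration shares and rate ratios. With no effect in one duration group and a 25–40% reduction in the other, false rejection is about 17–45% under independence and about 7–14% under exchangeable. A milder difference gives less, and a common effect gives none.

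Two stronger readings should be resisted. One is that the arm main effect of analysis C is thereby wrong: the argument concerns the heterogeneity test and the fitted time course, and a constant common arm effect is not distorted. The other is that the trial's conclusions depend on this test: no decision rule or power figure does. It is a cheap improvement.

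**What to change.** Add one sentence to analysis C: the arm-by-time test is read from a model that also includes arm by planned duration (3 vs 6 months), preferably with time by planned duration. This applies the duration cross-product term already foreseen in SAP 2.2 to this test. Define duration there as planned at randomization, because actual duration can be changed by early stopping afterwards. Name the GEE working correlation. Separate curves for 3- and 6-month patients are an optional presentation.

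The cost is one or two model terms built from an existing covariate, with no new data. In the 200-run simulations, the standard error of the arm-by-time term rose by 2–6% under exchangeable and fell by about 20% under independence, so the interval widens slightly only in the former case.
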